10.3 Statistical Analyses

10.3.1 Analysis of the Primary Efficacy Endpoint(s)

To test whether SHUTi engagement is associated with caregiving context, ordered logistic regressions assuming proportional odds will be fit for each caregiving-related user and environmental characteristic on SHUTi core completion, a 3-level ordinal

dependent variable (i.e., non-user vs. incomplete user vs. complete user). Models will control for a pre-specified set of covariates (i.e., age, household income, health literacy, mental and physical health related quality of life) that are not specific to caregivers, but affect both caregiving context factors^{35,72} and digital health engagement.^{77,87} Where the proportional odds assumption is violated ($p < .05$), follow-up sensitivity analyses will be conducted: two logistic regressions comparing proportional odds between non-users vs. users (incomplete and complete) and between non-completers (non-users and incomplete users) vs. complete users. Secondarily, we will assess whether caregiving-related user and environmental characteristics change during the course of the intervention period and test whether this change is related to engagement using a structural equation mediation modeling approach.⁸⁸ For users, we will also examine the associations between user and environment characteristics with SHUTi evaluations on the Internet Intervention Utility, Evaluation, and Adherence Questionnaires.

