10.2 Sample Size Determination

We will enroll up to about 130 high-intensity caregivers with insomnia into this single-arm (nonrandomized) trial. The minimum sample size to achieve is 100. Based on completion rates from [name] (University of Pittsburgh site PI) untailored Internet depression management program (non-users = 35%; incomplete = 40%; complete = 25%) and averages across SHUTi trials (non-users = 10%; incomplete = 25%; complete = 65%), we estimate that the sample in the proposed trial will break down as follows: 22% non-users, 33% incomplete users, 45% complete users. Assuming these response rates, the minimally detectable proportional odds (minOR) analyses at power = 80% with $\alpha = .05$ would be a moderate effect size⁹⁴ (minOR= 2.9) for a sample size of N = 100 based on rate of dichotomized predictor exposures (computed using the Whitehead formula⁹⁵ in R Hmisc⁹⁶; see Table below). Controlling for baseline values of cognitive mechanisms and covariates, an expected sample size of 78 users (33 incomplete + 45 complete) would have 80% power with $\alpha = .05$ to detect a small effect size of a user or environment characteristic on cognitive mechanisms at post ($R^2 = .04 < .10$).

Caregiving Strain			
N=100	Above Mdn	Below Mdn	% sample
Non-user	16	6	22%
User	34	44	78%
% sample	50%	50%	OR=3.4

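### The uptake and completion splits are reported only after a significant proportional odds test, which hides most moderate differences at N = 100 and inflates the uptake odds ratios that do get reported

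*Combined protocol and SAP*

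**What the plan says.** Section 10.3.1 fits one ordered logistic model per caregiving characteristic to three-level engagement, adjusted for five covariates (age, household income, health literacy, mental and physical health-related quality of life). "Where the proportional odds assumption is violated", judged at p < .05, it adds follow-up sensitivity analyses: "two logistic regressions comparing proportional odds between non-users vs. users", and a second contrast of non-completers with complete users. The proportional odds test is not named and its power is not given. No penalised or small-sample method is named for the binary models, so plain maximum likelihood is the natural reading, though it is an inference.

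Section 10.2 expects "22% non-users, 33% incomplete users, 45% complete users" and sizes the study on a common odds ratio ("minOR= 2.9) for a sample size of N = 100", "computed using the Whitehead formula"). The minimum N is 100 and the maximum about 130. The worked table for caregiving strain in the same section is a non-user vs user comparison, which is one of the splits that section 10.3.1 shows only if the test is significant.

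**The concern.** The plan treats never starting and stopping early as different behaviours. Section 8.1 gives non-users and users separate surveys, and section 10.3.2 looks for themes about uptake and about usage. A characteristic could therefore act differently on the two steps.

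A rule that shows the separate effects only after a significant test has two costs. If the test has little power, a real difference stays inside one averaged odds ratio. If it fires, the estimates shown are those that happened to look most different, so they are too extreme on average. The non-user split also rests on few people. At stake is how well the quantitative results inform the tailoring question in section 2.1, since a barrier to starting and a barrier to finishing would call for different changes.

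**Working it through.** **1. The plan's own figure.** Inputs from section 10.2: N = 100, outcome 22/33/45, power 80%, alpha .05 (two-sided assumed), predictor split 50/50 as in the strain table. Whitehead information:

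V = n1·n2·n / [3(n+1)²] × (1 − Σp³) = 50·50·100 / (3·101²) × (1 − 0.1377) = 8.169 × 0.8623 = 7.04.

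Minimum OR = exp[(1.960 + 0.842)/√7.04] = exp(1.056) = 2.87. This reproduces the stated 2.9; power at 2.9 is 80.7%. The strain table gives (16 × 44)/(6 × 34) = 3.45, printed as 3.4.

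**2. How often the rule triggers.** The plan gives no figure, so this was simulated with margins of 78% users and 45% completers and a binary 50/50 predictor. Unadjusted runs use a 1-df likelihood-ratio test. Adjusted runs use a 1-df Brant-type Wald test and assume five normal covariates, each with log OR 0.2 on engagement and correlation 0.3 with the predictor's latent score. Odds ratios are for non-use (uptake) and non-completion (completion). A dash means no figure is given.

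| True OR, uptake / completion | Triggers, unadjusted, N = 100 | Triggers, adjusted, N = 100 | Common OR (unadjusted) |
|---|---|---|---|
| 3.45 / 1.7 | 31–34% | – | about 2.1 |
| 2.9 / 1.5 | 29–34% | 20–23% | – |
| 2.0 / 1.0 | 31–34% | 23–25% | – |
| 2.9 / 1.0 | – | 47–51% | 1.40 |
| 3.45 / 1.0 | about 75% | 59% | about 1.5 |
| 2.9 / 0.67 (opposed) | – | 76% | 1.07 |

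At N = 130 the adjusted rates are 27% (2.9/1.5), 30–32% (2.0/1.0), 60–61% (2.9/1.0) and 86% (opposed).

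The rate depends on the non-user share. For 2.9/1.0 at N = 100, adjusted, it is 25% with 10% non-users and 78% with 35%, the two source rates in section 10.2. It also depends on the test: an omnibus version over all six slopes triggers in 38–39% for 2.9/1.0, and in about 8–9% of runs when proportional odds is true.

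When the common OR is 1.40, Whitehead power at N = 100 is Φ(0.336 × 2.654 − 1.960), about 14%.

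**3. Selection.** Average uptake OR (exponentiated mean log OR) among triggered trials, N = 100, true value 2.9:
- completion OR 1.0: about 3.5 unadjusted; adjusted, mean log OR 1.51–1.56, so OR 4.5–4.8;
- completion OR 1.5: about 4.2 unadjusted; adjusted, mean log OR 1.762, so OR exp(1.762) = 5.8.

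**4. Small-sample bias without selection.** 22 non-users over 6 slopes is 22/6 = 3.7 per slope. At a true log OR of 1.065, maximum likelihood averages about 1.19–1.206 at N = 100, which is 12–13% too large. The excess of about 0.13 is 0.2 of an SE of 0.64. At N = 130 the mean is 1.16, or 9% too large. Coverage is 93–95%. In the 2.9/1.0 case selection adds a further 0.32 (1.51 − 1.19) or more on the log scale, so it is the larger distortion. With 10% non-users the bias is 17%, and 75 of 3,000 runs did not converge. Firth fits average 1.065–1.08 at N = 100 and 1.07 at N = 130.

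**5. Precision.** The 95% limits lie exp(1.96 × 0.64) = 3.5-fold either side of the OR at N = 100, and exp(1.96 × 0.55) = 2.9-fold at N = 130. Power for OR 2.9 on the non-user split is about 45% and 56–57%.

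**The case against.** The hypothesis in section 10.1 concerns ordered engagement, and the common odds ratio answers it. The splits are labelled sensitivity analyses in a pilot. The misses are most frequent where they do least harm: with 3.45 and 1.7 both effects point the same way, and a common odds ratio near 2.1 lies between them. Where the common odds ratio misleads most, as with 3.45 vs 1.0 or opposed effects, the rule usually opens the splits. All of this stands.

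A reader might infer that the trial cannot tell a barrier to uptake from a barrier to completion. The documents do not support that. The splits are pre-specified, though conditionally. Section 8.1 asks non-users and users separately about barriers and their link to caregiving. Section 10.3.2 codes themes for uptake and usage, although its wording refers to users' responses.

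The objection does not remove the selection effect, and it gives no reason to withhold two odds ratios that the plan has already defined.

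**Conclusion.** The point holds as a reporting weakness. At N = 100 the rule shows the separate effects in only about 20–35% of trials with moderate differences, and what it shows for uptake is inflated by selection.

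Two stronger readings fail:
- Differing effects are not averaged away as a general matter. At 2.9 vs 1.0, adjusted, the rule is near a coin flip at N = 100 and triggers in about 60% of trials at N = 130; for larger or opposed differences it mostly triggers.
- Small-sample bias does not make the binary models unusable. It is 9–13% of the log odds ratio at the expected non-user share and affects only the non-user split, since the completion split is about 55 vs 45.

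Nothing here shows the primary model to be wrong. The simulated figures rest on the assumed 50/50 predictor, the covariate structure and the test used, none of which the documents fix for this purpose. The non-user count of 22 is the expectation at the minimum N; at 130 it would be about 29.

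**What to change.** Keep the common odds ratio as the primary result. For every characteristic, report both cumulative-split odds ratios with 95% intervals, adjusted for the same covariates, whatever the proportional odds test shows. Use Firth penalised logistic regression for the non-user split. Name the proportional odds test, say whether it covers the predictor alone or all slopes, and report its p-value without using it as a condition. Present the split estimates as descriptive.

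The cost is a longer results table and a little more analysis; no new data are needed. Firth removes most of the average bias but not the imprecision, so the non-user intervals will still be wide (about 3.5-fold either side at N = 100) and the text should say so.

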10.3.2 Analysis of the Secondary Endpoint(s)

To describe caregivers' barriers and motivations for SHUTi engagement, qualitative coding of users' open-ended survey responses from post-assessment will be conducted via Dedoose software. Data will be coded using two methods: First, using an a priori codebook to tag data according to whether it is: (a) specific to SHUTi; (b) specific to CBT-I, but not exclusively SHUTi; or (c) specific to digital health interventions, but not exclusively SHUTi. This will facilitate examination of the extent to which caregiver-specific tailoring recommendations are specific to SHUTi versus generalizable to other evidence-based psychosocial digital health interventions. Responses will next be coded inductively using thematic text analysis⁸⁹⁻⁹¹ to identify themes related to caregivers' barriers to and motivations for SHUTi uptake and usage, as well as how caregiver-specific tailoring may affect each of those constructs. Each response will be coded by two independent coders with discrepancies resolved by consensus. The coding team will iteratively determine a set of codes; identify, review and name themes; and synthesize data into final actionable recommendations for tailoring SHUTi and other digital health interventions for caregivers.

Findings and resultant recommendations will be returned to caregivers for synthesized member checking⁹²:

- (1) A concise report of results will be sent to caregivers;
- (2) Caregivers will review the report and comment on how results compare/contrast with their experiences and needs; and
- (3) Caregivers' returned responses will be coded to ascertain level of resonance between caregivers' reported experiences and the researchers' original results. Findings and recommendations will be revised according to synthesized member checking results.

To test whether the effects of SHUTi on cognitive mechanisms (i.e., more adaptive sleep beliefs, internalized sleep locus of control) are associated with caregiving context, a continuous regression model will be computed for each user and environment characteristic on each cognitive mechanism assessed at post, controlling for pre-assessment level of the mechanism.⁹³ Caregivers who are SHUTi users (incomplete and complete; not non-users) will be included, and models will control for level of SHUTi engagement and pre-specified covariates, with significance set at $p < .05$.

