8 STUDY ASSESSMENTS AND PROCEDURES

8.1 Study Materials and Methods

Participating caregivers will be instructed on how to complete the pre-assessment battery of online questionnaires using either computer or mobile device as the participant prefers. Estimated completion times are 30 minutes for questionnaires. Upon completing questionnaires, participants will complete 10 daily sleep diaries within 14 days. Participants will be compensated \$40 upon pre-assessment completion.

After participants complete pre-assessment, they will receive access to SHUTi. Participants will be emailed a unique username and password in order to log on and securely access SHUTi for 9 weeks. The intervention can be accessed via an Internet enabled device, including a computer, tablet, or smartphone. At the start of week ten, regardless of intervention progress, participants will be instructed to complete their online post assessment.

Non-users' (i.e., those who completed 0 SHUTi Cores) post-assessment will include an open-ended survey regarding barriers to SHUTi adoption, the extent to which barriers were related to caregiving, and what modifications may have increased their motivation to try SHUTi. Users' (i.e., those who completed 1 or more SHUTi Cores) post-assessment will include an open-ended survey assessing SHUTi usage barriers and motivations, the extent to which these were related to caregiving, and how tailoring may improve usage by increasing salience to caregivers. SHUTi users will also complete 10 daily sleep diaries in 14 days as part of post-assessment. Participants will be compensated \$40 upon post-assessment completion.

Caregivers who agree to be contacted for follow-up will be returned a concise report of results from the analyses as part of synthesized member checking procedures, where caregivers will be asked to review the report and comment on how results compare/contrast with their experiences and needs.

Sources of research materials:

The sources of research material will include:

- (1) self-report questionnaires completed over the Internet (including caregiving-related user- and environment characteristics; as well as demographics, sleep, self-efficacy and other health/psychosocial constructs);
- (2) telephone interview to inquire about sleep problems, insomnia treatment history, and computer/Internet usage;

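### The qualitative coding rule in Section 10.3.2 names only users' answers, so the non-user survey on adoption barriers has no stated analysis

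*Combined protocol and SAP*

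**What the plan says.** The secondary objective in Section 3 is to describe what hinders and what motivates caregivers' engagement with SHUTi. Open-ended feedback is one of its two endpoints, and Section 3 does not restrict it to any engagement group. Section 2.1 says the description will come from caregivers' answers to open-ended surveys, again without restriction.

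Section 8.1 sets up two such surveys at post-assessment:

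- "Non-users' (i.e., those who completed 0 SHUTi Cores) post-assessment will include an open-ended survey regarding barriers to SHUTi adoption". It also asks how far the barriers were related to caregiving and what changes might have made these caregivers more willing to try the program.
- "Users' (i.e., those who completed 1 or more SHUTi Cores) post-assessment will include an open-ended survey assessing SHUTi usage barriers and motivations". It also asks how tailoring might improve usage.

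The measures table in Section 8.1 lists open-ended feedback for both groups, with separate surveys. It marks the structured utility and barriers questionnaires as being for SHUTi users only.

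The detailed analysis rule for the open-ended data is in Section 10.3.2: "qualitative coding of users' open-ended survey responses from post-assessment will be conducted via Dedoose software". The inductive coding step is meant "to identify themes related to caregivers' barriers to and motivations for SHUTi uptake and usage". Later in the same section, the regressions on cognitive mechanisms carry an explicit restriction: "Caregivers who are SHUTi users (incomplete and complete; not non-users) will be included".

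**The concern.** The coding rule names the responses of one group only, and that group has a definition. Taken literally, the non-user survey would be collected and never coded.

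That matters because the two surveys ask different things. The one on adoption goes to caregivers who completed no Core. The one for users is described as being about usage. Under the literal rule, the initial themes and tailoring recommendations on uptake would come only from people who had already taken the program up, answering a survey about using it. Since the structured utility and barriers questionnaires are restricted to users, the open-ended survey is also the only instrument on SHUTi barriers that non-users receive at post-assessment.

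**Working it through.** The point is textual. The passages are set side by side first, and the group sizes follow.

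**What the word means in this plan**

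- Section 8.1, introducing these surveys: users completed 1 or more Cores and non-users completed 0.
- Section 10.2: "an expected sample size of 78 users (33 incomplete + 45 complete", with the 22% non-users counted separately.
- Section 10.3.1, sensitivity analyses: "comparing proportional odds between non-users vs. users (incomplete and complete".
- Section 10.3.2, mechanism regressions: users are the incomplete and complete groups, with non-users expressly left out.

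Wherever the word is set against non-users, it means at least one Core completed.

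**What the coding rule would need to cover**

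| Place | Scope |
|---|---|
| Section 3, secondary objective | caregivers |
| Section 2.1, rationale | caregivers' answers to open-ended surveys |
| Section 8.1, measures table | both groups, separate surveys |
| Section 10.3.2, themes sought | caregivers; uptake and usage |
| Section 10.3.2, data to be coded | users |

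Only the last row is narrower than the rest. The questionnaire endpoint of the same objective is handled in 10.3.1 and is also limited to users: "For users, we will also examine the associations between user and environment characteristics with SHUTi evaluations". No section expressly assigns the non-user survey to an analysis.

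**Size of the group left out under the literal reading**

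Inputs from Section 10.2: a minimum of 100 and a maximum of about 130 caregivers; planned shares of 22% non-users, 33% incomplete users and 45% complete users; source non-user rates of 35% (the depression program) and 10% (SHUTi trials).

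The planned shares are the simple means of the two sources:

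- non-users (35 + 10)/2 = 22.5%
- incomplete users (40 + 25)/2 = 32.5%
- complete users (25 + 65)/2 = 45%

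These agree with the stated 22/33/45 after rounding.

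Group size = share × N:

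| | N = 100 | N = 130 |
|---|---|---|
| Non-users at 22% | 22 | 28.6, about 29 |
| Non-users at 10% | 10 | 13 |
| Non-users at 35% | 35 | 45.5, about 46 |
| Users at 78% (the coded group) | 78 | 101.4, about 101 |

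These are counts before post-assessment non-response. The documents give no response rate, so they are upper limits on the surveys available.

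**The case against.** The strongest reply is that the plan, read as a whole, already means both surveys. The sentence containing the disputed word opens by referring to caregivers. The themes sought include uptake, which makes most sense if the adoption survey is coded. Section 2.1 sets no limit to users, and the open-ended row of the measures table has no users-only mark. Where the authors want non-users out, they say so: in the mechanism regressions, in the questionnaire analysis and in the table footnote. The plan also uses the word generically, as in user characteristics, so a loose reading is available.

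Most of this stands as evidence of intent, and a drafting slip is the likelier explanation. It does not settle the text. Here the word describes survey responses, and Section 8.1 separates those surveys by user status. A coding team following 10.3.2 as written would have grounds to leave the non-user survey aside.

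A second reply is that member checking brings non-users in. Section 10.3.2 does say that returned comments are coded and that findings are revised in their light, so non-users could change the recommendations at that stage. That route reaches only caregivers who agree to follow-up contact, and it collects reactions to a report. It does not analyse non-users' own survey answers.

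**Conclusion.** The concern holds, at modest severity. As written, the coding rule in 10.3.2 is narrower than the objective, the rationale and its own aim, and it leaves the non-user survey without an analysis. Under the literal reading, about 22 of 100 or 29 of 130 caregivers are left out at the planned rate, and 10 to 35 of 100 or 13 to 46 of 130 across the two source rates.

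These figures assume the Section 10.2 engagement shares and full return of the post-assessment. They describe the size of the group, not a demonstrated loss, because the team may well intend to code both surveys. Confidence is high on the mismatch in wording; how the coding team would act on it is not known. No hypothesis test, sample size or primary endpoint is affected.

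**What to change.** In Section 10.3.2, change the description of the data to be coded so that it reads: *open-ended survey responses from both non-users and users*. Keep the codebook and the two-coder procedure as they stand. Labelling themes by the survey they came from is advisable, since the items differ, but it is optional. If the narrow reading was in fact intended, the objective and the reference to uptake would have to be narrowed instead.

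The cost is one phrase. There is no new data collection. The extra work is double coding of at most 22 to 29 non-user surveys at the planned rate: 22 × 2 = 44 to 29 × 2 = 58 survey readings. Across the source rates it is 10 × 2 = 20 to 46 × 2 = 92 readings. All of these fall with non-response.

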emotional and physical well-being.^{2,3} Support from family members to seriously ill individuals is critical to the sustainability of the U.S. healthcare system,¹⁴ but it places a significant strain on these caregivers. Insomnia is among the most common, distressing, and impairing psycho-physiological issue for caregivers, who report this problem more commonly than non-caregivers.^{15,16} Compared to about 33-50% in the general population,¹⁷ up to 90% of caregivers report sleep impairment,¹⁸ although rates have varied by contexts – for example, 27% in Parkinson's caregivers,¹⁹ 50-75% in cancer,²⁰⁻²² and 63-68% in dementia.^{18,23,24} Sleep impairment contributes to caregivers' anxiety, depression, and physical morbidity,^{21,25-29} which affect caregivers more severely than those in the general population.³⁰⁻³³ Moreover, caregivers' poor sleep also ultimately affects their care recipients. Because it increases their distress, sleep-deprived caregivers are more likely to exhibit harmful caregiving behavior³⁴ and less able to meet the practical and social-emotional needs of the care recipient.^{35,36} Additionally, care recipients' sleep disturbance is interrelated with their caregivers'.^{37,38} Accessible and effective insomnia interventions for caregivers are therefore important to the well-being of both caregivers and care recipients. Although such interventions are effective, they suffer from low enrollment, high dropout, and limited reach to caregivers who already have inadequate healthcare access, like caregivers from lower SES or those in rural areas.³⁹⁻⁴³ Digital health interventions can lower barriers to entry to supportive care for caregivers as they are conveniently accessible anywhere and anytime from an Internet-enabled device. Indeed, caregivers express strong interest in Internet interventions because of their convenience.⁴⁴⁻⁴⁶ Multiple existing, efficacious digital health interventions may effectively address caregivers' psychosocial needs. For example, Sleep Healthy Using the Internet (SHUTi), developed by [name], is an NCI designated research-tested intervention that delivers cognitive-behavioral therapy for insomnia (CBT-I).^{47,48} Most digital health interventions tested among caregivers, however, have been developed *de novo* for specific caregiving contexts.⁴⁹⁻⁵⁴ Tailoring interventions in this way is rooted in behavior change theory: tailoring to a user's characteristics increases information salience, which increases a user's attention to information, which ultimately increases the likelihood that the information will motivate behavior change.⁸ When tested empirically, tailoring typically adds only small gains in outcomes relative to generic materials, although gains are typically maintained over time.^{10,55,56} The decision to tailor, and how to tailor, must balance expected benefits of increased specificity against reduced reach and increased costs (time and financial). The implicit assumption underlying existing research – where *de novo* interventions are developed for caregivers – is that caregivers have different deficits, risk factors, and needs from non-caregivers. There is reason to believe this is true and that caregiving has unique psychological and environmental factors that would affect use and impact of insomnia interventions specifically, and digital health interventions broadly. Specific to insomnia interventions, caregivers' insomnia can be perpetuated by worry about the negative impact of sleep loss on their ability to meet the demands of caregiving and a feeling of helplessness to improve their sleep due to their caregiving responsibilities.^{22,28,57} Indeed, caregivers do frequently need to organize their sleep around the needs of the care recipient³⁸ and often need to support the care recipient at night with symptom management or nighttime behavioral issues.^{22,28} When considering digital health interventions more broadly, research repeatedly highlights primary barriers to caregivers' help-seeking being their self-sacrifice – the de-prioritization of caregivers' own needs behind the needs of the care recipient, particularly prominent among high-intensity caregivers – and caregivers' guilt when they do prioritize their needs.⁵⁸⁻⁶¹ Caregivers' often busy and chaotic schedules – also particularly true of high-intensity caregivers – likewise commonly get in the way of their ability to commit to consistently

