4 STUDY DESIGN

4.1 Overall Design

This study comprises a single-arm (nonrandomized) clinical trial with quantitative and qualitative data collection.

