10 STATISTICAL CONSIDERATIONS

10.1 Statistical Hypotheses

Primary hypothesis: caregivers' engagement with SHUTi (i.e., being a non-user vs. incomplete user vs. complete user) will be associated with their caregiving-related user characteristics (i.e., caregiving strain, self-efficacy, and guilt) and environment characteristics (i.e., proximity to care recipient; care recipient functional, cognitive, and behavioral status; caregiving tasks).

Secondary hypothesis: the effects of SHUTi on cognitive mechanisms of change targeted by SHUTi (i.e., more adaptive sleep beliefs, internalized sleep locus of control) will differ by caregiving-related user characteristics (i.e., caregiving strain, self-efficacy, and guilt) and environment characteristics (i.e., proximity to care recipient; care recipient functional, cognitive, and behavioral status; caregiving tasks).

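### The Aim 2 models adjust a non-randomised comparison for one error-prone pre score, so their .05 tests can be too liberal; one measurement-error sensitivity analysis should be pre-specified

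*Combined protocol and SAP*

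**What the plan says.** All references are to the combined protocol and SAP.

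- **Design (4.1).** "This study comprises a single-arm (nonrandomized) clinical trial with quantitative and qualitative data collection". Nothing balances baseline sleep beliefs or sleep control across levels of a characteristic.
- **Model (10.3.2).** One continuous regression per characteristic "on each cognitive mechanism assessed at post, controlling for pre-assessment level of the mechanism". Only users enter. The models also adjust for engagement level and the pre-specified covariates, and significance is set at .05.
- **Covariates (10.3.1).** These are "age, household income, health literacy, mental and physical health related quality of life". None is a second measure of either mechanism.
- **Measurement (table in 8.1).** The sleep beliefs and sleep locus of control scales are each given once at pre and once at post, the latter to users only.
- **Interpretation (10.1).** The secondary hypothesis is that SHUTi's effects on the mechanisms "will differ by caregiving-related user characteristics" and by environment characteristics. It states no direction.
- **Reason to expect correlation with baseline (2.2).** Caregivers' insomnia can be maintained by worry about sleep loss and by "a feeling of helplessness to improve their sleep due to their caregiving responsibilities".

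For Aim 2 the documents give no scale reliability, no measurement-error correction and no caution about baseline differences.

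**The concern.** Adjusting for a pre score removes a baseline difference fully only if that score is measured without error. A self-report score is not. When the predictor is randomised this costs only precision, because predictor and true baseline are unrelated. Here they may be related: strain or guilt plausibly goes with worry and helplessness about sleep. The unremoved part of the baseline difference then appears in the characteristic's coefficient, which 10.1 reads as a difference in SHUTi's effect.

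This is separate from the lack of a control arm, since it also affects the plain statement that change over time differs by context. Section 2.1 says the findings will direct how SHUTi is tailored for caregivers, so a leftover baseline difference could be mistaken for a reason to tailor.

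**Working it through.** **1. The plan's own figure.** Section 10.2 states that "an expected sample size of 78 users (33 incomplete + 45 complete) would have 80% power" for an R² of .04. With a noncentral F test of one coefficient at n = 78, 80% power needs f² of about .103, a partial R² of about .09. An incremental R² of .04 gives that f² only if 1 − R²(full) = .04/.103 = .39, so the whole model must explain about 61% of the post-score variance. That value is not stated, so the figure is neither confirmed nor refuted. Only n = 78 is carried forward.

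**2. Inputs.** From the documents: n = 78, the model form, and .05 (taken as two-sided). Assumed, because the documents are silent: pre-score reliability *rel* of .7 to .9, and correlation ρ of .2 to .5 between the characteristic X and the *true* baseline T.

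**3. Expected coefficient when everyone changes equally.** Scale T to variance 1. Pre = T + error and post = T − constant + error, each with error variance (1 − rel)/rel. Then

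- λ = (1 − ρ²) / [(1 − ρ²) + error variance]
- coefficient on X = ρ(1 − λ)

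For ρ = .4 and rel = .8:

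- Error variance = .2/.8 = .25; λ = .84/1.09 = .771; coefficient = .4 × .229 = .092 true-score SD per SD of X, where the right answer is 0.
- Variance of X left after the pre score = 1 − .16 × .8 = .872, so the false signal explains .092² × .872 ≈ .0073.
- Residual variance = .84 × .229 + .25 = .443.
- Partial R² = .0073/(.0073 + .443) = .016; incremental R² = .0073/1.25 = .006.
- Noncentrality = 78 × .0073/.443 ≈ 1.3, which gives rejection in about 20% of trials at a nominal 5%.

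The coefficient takes the sign of ρ. It is zero if ρ = 0 or rel = 1, and in simulation the planned model then rejects in about 5% of runs, which isolates the cause. At ρ = .2 the same formula gives about 7% (rel .9) to 10% (rel .7).

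**4. Simulation, n = 78, six covariates, equal change for all.** Type I error of the planned model:

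| Reliability | Covariates unrelated to X and T: ρ = .3 / .4 / .5 | One distress-like covariate: ρ = .3 / .4 / .5 |
|---|---|---|
| .9 | 9 / 13 / 18% | 6 / 9 / 13% |
| .8 | 12 / 18 / 28% | 7 / 11 / 20% |
| .7 | 15 / 25 / 37% | 8 / 14 / 25% |

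The distress-like covariate is assumed to correlate .5 with X and .4 with T, with reliability .85. At ρ = .2 it brings the error to about 5%, because .5 × .4 = .20 accounts for the whole link. A repeat run gave 26% in the bottom right cell.

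**5. Individual variation in change.** Adding change variance of 0.3 SD², unrelated to X, to the distress-covariate case gives 6 / 9 / 14% at reliability .8, and at most about 20% over the range.

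**6. Which correction works.**

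| Setting (X has no effect of its own) | Planned | Change score | Error-corrected pre score |
|---|---|---|---|
| Equal change | 9–37% | about 5% | 6–8% |
| Improvement proportional to baseline (slope .7, ρ = .4) | 8–15% | 16–35% | 5–7% |

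In a further run with slopes .8 and .6, the change score rejected in 9 to 46% and the planned model in 5 to 30%. The change score was the worse of the two in 10 of 12 settings; the exceptions were both at reliability .7 with slope .8.

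**The case against.** The strongest reply is that the planned covariates already do much of the work. Distress is the obvious shared correlate of strain or guilt and of negative sleep beliefs. Section 10.3.1 adjusts for mental health quality of life, and the table in 8.1 lists a four-item distress questionnaire among the covariates. This stands: it is why the second column of the simulation table is lower, and what matters is the correlation left after the covariates.

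Three further points stand in part.

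- Section 2.2 describes caregivers as a group. It does not show a gradient across strain or guilt, still less across proximity or care-recipient function. A correlation is plausible for some characteristics and unquantified for all.
- Identical change for everyone is an extreme null, and realistic variation lowers the error rate.
- This is a secondary aim of a pilot with no control arm, where effects of SHUTi are not identified in any case.

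A reader might infer that any characteristic correlated with baseline will look related to response. The figures do not support that: within the assumed range most such tests do not reject. A reader might also infer that the bias favours the result the trial is looking for. The hypothesis in 10.1 is non-directional, and the bias follows the sign of an unknown correlation.

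None of this restores the nominal 5% for a characteristic that keeps a correlation with true baseline after adjustment.

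**Conclusion.** The concern holds as a bias in expectation and an inflated error rate, of uncertain size. With 78 users, reliability .7 to .9 and ρ of .2 to .5, type I error at nominal 5% is about 7 to 37% if the covariates are unrelated to characteristic and baseline. It is about 5 to 26% if one of them absorbs part of the link, and lower again with individual variation in change. The upper figures need low reliability, a strong correlation and uninformative covariates together, and should not be read as the expected rate.

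ρ here refers to the true baseline. The correlation seen with the observed pre score is smaller by a factor √rel, so an observed .5 at reliability .7 means a true .5/√.7 = .60, beyond the range used.

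A reader might conclude that the planned model should give way to change scores, or that only a corrected model may support a claim. Neither follows: the change score does worse in most settings where improvement depends on baseline, and the correction itself rests on an assumed reliability.

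**What to change.** Keep the planned model as the Aim 2 analysis and add to 10.3.2:

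1. One sensitivity analysis per characteristic and mechanism: the same model with the pre score corrected for measurement error (errors-in-variables or regression calibration), over a stated reliability range such as .7 to .9. A range is needed because internal consistency from the trial's item data misses occasion-to-occasion error.
2. A table of each characteristic's correlation with the pre score, adjusted for the covariates, so the reader can see where the issue can arise.
3. A reporting rule: an association that does not survive the correction is described as possibly due to baseline differences.

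Do not use a change-score model as the check.

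Cost: SAP wording, some analysis time and wider intervals for the corrected estimates. With eight characteristics and two mechanisms there are at least 8 × 2 = 16 further estimates, each repeated over the reliability range. The correction is not exact at this sample size, as its 5 to 8% above shows.
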